4.0 Eligibility Criteria

4.1 Inclusion Criteria (to be assessed prior to procedure)

- Age 18 years or older
- Speaks and reads in English
- Able to consent on their own
- Will undergo any intrauterine procedure using the Carevix[™] (for exposure group) or using Tenaculum (for Control Group)
- Up to 20 providers performing this procedure
- Provider is willing to use Carevix[™] for scheduled procedure

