3.2 Secondary Outcome Measures

3.2.1 Secondary outcome measures: To assess provider-reported bleeding, ease of use and provider satisfaction with the device, the provider will complete a questionnaire following the patient's completion of their portion of the questionnaire (Attachment #2). This takes, on average, 2 minutes to complete.

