5.0 Study Design

Aspivix, the company that created Carevix[™], launched the Ambassador Program, a 3-6 month program with free of charge devices for clinics willing to test Carevix[™] in multiple intrauterine procedures. Our clinic, Coleman Center, will conduct a prospective cohort study for 3-6 months where patients who qualify via inclusion criteria who are also receiving an intrauterine procedure (endometrial biopsy, IUD insertion, manual aspiration, etc) on the exposure (Carevix[™]) arm will have the opportunity to receive the Carevix[™] device for cervical stabilization, per provider preference (i.e., providers may decline to use Carevix[™] for endometrial biopsy).

Once 25 participants have received Carevix[™], recruitment for the control (tenaculum) arm will begin. Participants will receive the standard of care device if cervical stabilization is required. Each participant will be provided with a study information sheet and sign a consent form. They will then undergo their planned procedure, using the assigned device.

Following completion of their procedure, they will also agree to fill out a survey about their experience, which takes about 1 minute to complete. The provider performing the procedure will finish the survey with provider-specific questions about bleeding, ease of use and satisfaction. The purpose of this study is to compare Carevix[™] to the tenaculum and determine if the Carevix[™] shows similar results in the United States population as it has in the European study and with all intrauterine procedures.

*Once 25 of 30 patients received CarevixTM, will commence control group collection N = 30

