7.0 Study Procedures

Any intrauterine procedure already scheduled will otherwise proceed accordingly as part of clinical care. During the enrollment, patients who fit above inclusion criteria and are scheduled for an intrauterine procedure may be offered the opportunity to participate in this program and trial the new Carevix[™] device during the exposure recruitment period and complete a short survey. If the patient consents to the use of Carevix[™] Ambassador program, the suction-based cervical stabilizer will be used on their cervix to stabilize the cervix during the procedure instead of the traditional tenaculum. If the patient or provider opts out of the use of Carevix[™], they will be asked if they'd like to participate in the study with the tenaculum. During the tenaculum enrollment phase, patients will receive the standard of care device and complete a short survey.

Following completion of the procedure, the patient will then fill out the patient-based survey. Following the completion of the patient's questions, the provider will then fill out the provider-based survey.

The questionnaire for the Carevix[™] Ambassador program will be stored within the Aspivix company database (all questions are HIPAA compliant and do not reveal PHI). The survey is labeled as originating from Indiana University for easy access to only our patient data.

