12.0 Statistical Considerations

We performed sample size/power calculations with the primary outcome of pain (visual analog scale) at the time of Carevix[™]/tenaculum use. Thirty participants per group (total N=60) are needed to achieve at least 80% power and a two-sided 5% significance level. Descriptive characteristics of those in the Carevix[™] and control groups will be compared using standard statistical testing such as Chi-square and t-tests. Differences in outcomes between the device and control groups will similarly utilize standard testing.

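### Nothing ties the same providers to both arms and no analysis adjusts for provider, so provider differences can be counted as a device effect

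*Combined protocol and SAP*

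**What the plan says.** - **Who may treat.** Section 4.1 lists "Up to 20 providers performing this procedure" with no minimum, no number per arm and no cap per provider. The next item on the same list is "Provider is willing to use Carevix" for the scheduled procedure. The list covers both groups.
- **How the device is chosen.** Section 5.0 describes a prospective cohort at one clinic in which eligible patients may receive Carevix "for cervical stabilization, per provider preference". Its one example is a provider declining the device for endometrial biopsy.
- **What happens on refusal.** Section 7.0 has a rule that begins "If the patient or provider opts out of the use of" Carevix; it invites the patient to join the study with the tenaculum.
- **Timing.** Section 6.0 enrolls 25 of the 30 Carevix patients before planned control enrollment begins. The last 5 run alongside the 30 controls. Section 15.0 gives about six months to each group.
- **Who rates.** Under section 3.2 a provider questionnaire is used "To assess provider-reported bleeding, ease of use and provider satisfaction with the device", and section 5.0 says that the provider performing the procedure completes it. Bleeding also appears in the primary objective in section 2.1.
- **Analysis.** Section 12.0 compares outcomes with standard tests, naming Chi-square and t-tests for the descriptive comparisons. It has no provider term, stratum or allowance for clustering.

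**The concern.** In a non-randomized comparison the two arms should differ in the device and in as little else as possible. Here the person who handles the device may affect the patient's pain, and that person also scores bleeding, ease of use and satisfaction. If gentler or more lenient providers are concentrated in one arm, pain and every provider-rated outcome can shift, and the planned tests attribute the shift to the device.

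The plan leaves two routes open. One is chance: a modest number of providers with uneven case counts in two largely successive enrollment periods. The other is systematic: a provider who declines Carevix can still supply tenaculum patients, so providers less inclined to use the new device may appear only among the controls. More patients would not remove that second kind of difference.

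Timing matters for the remedy. If the arms shared no providers, no analysis could separate device from provider, so overlap has to be secured during enrollment.

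**Working it through.** **The plan's own figure.** Section 12.0 states "Thirty participants per group (total N=60) are needed" for "at least 80% power and a two-sided 5% significance level", based on the "primary outcome of pain (visual analog scale) at the time of" device use. It gives no difference or SD, so 30 cannot be derived forward. Solved backward with the normal formula, the detectable difference is (1.960 + 0.842) × √(2/30) = 0.723 SD; the t-test version gives 0.736 SD. These are implied values, not values that the plan states.

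**Assumptions, none of them in the documents.** Total SD 1; a random provider effect with intraclass correlation ICC; k = 5 equally loaded providers per arm with 6 patients each; c of the 5 shared between arms.

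**Variance of the arm difference.**

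Var = 2(1 − ICC)/30 + 2·ICC·(5 − c)/25

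The first term is what remains when every provider treats equal numbers with each device. The second is the provider contribution. Dividing Var by the first term gives the ratio against a balanced within-provider comparison:

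- No provider shared (c = 0): 1 + 6·ICC/(1 − ICC)
- 4 of 5 shared (c = 4): 1 + 1.2·ICC/(1 − ICC)

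| ICC | Ratio, none shared | Ratio, 4 of 5 shared |
|---|---|---|
| 0.05 | 1 + 0.30/0.95 = 1.32 | 1 + 0.06/0.95 = 1.06 |
| 0.1 | 1 + 0.60/0.90 = 1.67 | 1 + 0.12/0.90 = 1.13 |
| 0.3 | 1 + 1.80/0.70 = 3.57 | 1 + 0.36/0.70 = 1.51 |

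At ICC 0.1 with none shared, the provider part of the arm difference has SD √(2 × 0.1/5) = 0.20. That is about 28% of the 0.72 SD the trial can detect.

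**False-positive rate of an unadjusted t-test, 30 against 30, no device effect (simulated).**

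| ICC | None shared | 4 of 5 shared | Full balanced overlap |
|---|---|---|---|
| 0.05 | about 8% | about 5% | at or below 5% |
| 0.1 | about 11% | about 5% to 6% | at or below 5% |
| 0.3 | about 23% | about 6% | at or below 5% |

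**Hand check at ICC 0.1, none shared.** The within-arm variance has expectation 0.9 + 0.1 × (30/29) × (4/5) = 0.983, so the t-test uses a standard error of about √(2 × 0.983/30) = 0.256. The true SD of the difference is √(0.06 + 0.04) = 0.316. The critical value 2.00 then corresponds to 2.00 × 0.256/0.316 = 1.62 true SDs, a two-sided probability of about 10.5%, in line with the simulation.

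**Sensitivity to the number of providers, none shared, ICC 0.1.** The rate is about 16% with 3 providers per arm and about 7% with 10.

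**The case against.** **The willingness criterion.** Read as applying to both arms, it would confine the controls to providers who are willing to use Carevix. At a single clinic where the tenaculum is the standard device, those providers would probably treat in both arms. This carries weight: substantial overlap is likely. But the criterion does not make any provider contribute to both arms or balance the counts. It also conflicts with the opt-out route in section 7.0, under which a provider who declines can supply a control. The two sections must be reconciled.

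**Preference by procedure.** The only example in section 5.0 is declining for one type of procedure. That mainly shifts the procedure mix and does not show that different providers serve each arm. This is also correct. A reader might infer that the arms will come from separate sets of providers; the documents permit that but do not say it, so the no-overlap figures are an upper case.

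**Loss of power.** A reader might infer that power collapses from a planned level. The plan states no effect size. With no shared providers and a true difference of 0.736 SD, the unadjusted t-test still rejects about 76% of the time at ICC 0.1 and about 72% at ICC 0.3. The main harm is false positives and confounding.

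**Balance as the only cure.** This would go too far. Where providers overlap, a provider term removes additive provider differences without equal counts, though less efficiently. Exact quotas would be too rigid with up to 20 providers and 60 patients.

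**Conclusion.** The gap is real. As written, the plan allows provider differences to be read as a device effect on pain and on every provider-rated outcome, and neither enrollment nor analysis guards against it.

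Its size cannot be known from the documents. With most providers shared, which a single clinic makes plausible, chance imbalance does little: a false-positive rate of about 5% to 6% and a variance ratio of 1.1 to 1.5 (ICC 0.1 to 0.3). With no sharing, the rate is about 8% to 23% and the ratio 1.3 to 3.6 (ICC 0.05 to 0.3). These figures rest on the assumed ICC, on equal loads and on 5 providers per arm. They cover random provider effects only; systematic self-selection of providers would add bias on top.

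The change should be made because overlap cannot be created after enrollment. It is also unclear whether the problem could be diagnosed later. Section 13.0 mentions a location selector and date-time matching for the Carevix survey, and the questionnaire is not available to show whether provider identity is captured.

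**What to change.** - **Data (13.0).** Record a provider code for every patient in both the Aspivix and RedCap datasets.
- **Enrollment (6.0).** Recruit controls from providers who performed Carevix cases. Use each provider's Carevix count as a target, not a hard quota. Keep a tally in RedCap and update it as the last five Carevix cases accrue.
- **Consistency (4.1 and 7.0).** Reconcile the willingness criterion with the opt-out route, and state how patients of a declining provider are counted in the analysis.
- **Analysis (12.0).** Report arm-by-provider counts. Make the pain comparison provider-adjusted, with provider as a stratum or as a fixed or random effect, and with low-volume providers pooled by a rule set in advance. Give the unadjusted test as a sensitivity analysis, and use controls from providers with no Carevix case only in a sensitivity analysis.

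**Cost.** Protocol wording, one data field and a tally; the total stays at 60. The last few controls may accrue more slowly if a provider leaves or does few procedures. Adjustment loses precision when many providers contribute few patients: about 30% more variance with 20 unevenly loaded providers whose counts are not matched. The targets and the pooling limit that loss.

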4.2 Exclusion Criteria (to be assessed by provider at time of procedure)

- Vaginal bleeding of unknown origin
- Cervix less than 26 mm in diameter
- Nabothian cyst on anterior lip of cervix
- Cervical myomas
- Cervical abnormalities/shape
- Pregnant

4.3 Other Criteria

4.3.1 If the patient does not require ANY cervical stabilization after consent into either study arm, the subject status will be considered **ineligible** and the patient will not be required to complete any surveys.

[figure not shown]
5.0 Study Design

Aspivix, the company that created Carevix[™], launched the Ambassador Program, a 3-6 month program with free of charge devices for clinics willing to test Carevix[™] in multiple intrauterine procedures. Our clinic, Coleman Center, will conduct a prospective cohort study for 3-6 months where patients who qualify via inclusion criteria who are also receiving an intrauterine procedure (endometrial biopsy, IUD insertion, manual aspiration, etc) on the exposure (Carevix[™]) arm will have the opportunity to receive the Carevix[™] device for cervical stabilization, per provider preference (i.e., providers may decline to use Carevix[™] for endometrial biopsy).

Once 25 participants have received Carevix[™], recruitment for the control (tenaculum) arm will begin. Participants will receive the standard of care device if cervical stabilization is required. Each participant will be provided with a study information sheet and sign a consent form. They will then undergo their planned procedure, using the assigned device.

Following completion of their procedure, they will also agree to fill out a survey about their experience, which takes about 1 minute to complete. The provider performing the procedure will finish the survey with provider-specific questions about bleeding, ease of use and satisfaction. The purpose of this study is to compare Carevix[™] to the tenaculum and determine if the Carevix[™] shows similar results in the United States population as it has in the European study and with all intrauterine procedures.

*Once 25 of 30 patients received CarevixTM, will commence control group collection N = 30

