6.0 Enrollment

We intend to enroll twenty-five evaluable Carevix subjects prior to commencing the enrollment of the control-group tenaculum subjects. An additional five Carevix subjects (for a total of N=30) will be concurrently enrolled while accruing the thirty additional tenaculum subjects for a total enrollment of N=60.

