15.0 Follow-up and Record Retention

The study will last about 1 year (6 months for Carevix[™] exposure group and approximately 6 months for the control group (e.g. tenaculum). The record retention will be indefinite.

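### Sections 5.0 and 6.0 hold back control recruitment until 25 Carevix subjects, but 7.0 invites Carevix opt-outs to join with the tenaculum, so the 30 controls may mix two populations

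*Combined protocol and SAP*

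**What the plan says.** **When controls start.** Section 5.0: "Once 25 participants have received Carevix[™], recruitment for the control (tenaculum) arm will begin". Its closing footnote repeats the 25-of-30 trigger. Section 6.0: "We intend to enroll twenty-five evaluable Carevix subjects prior to commencing the enrollment of the control-group tenaculum subjects". The remaining five Carevix subjects "will be concurrently enrolled while accruing the thirty additional tenaculum subjects for a total enrollment of N=60". Section 15.0 lists the two periods separately: "6 months for Carevix[™] exposure group and approximately 6 months for the control group".

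**What happens to opt-outs.** Section 7.0 first says that eligible patients may be offered the chance to "trial the new Carevix[™] device during the exposure recruitment period and complete a short survey". It then says of cases where the patient or the provider opts out: "they will be asked if they'd like to participate in the study with the tenaculum". The sentence after that describes the tenaculum enrolment phase as a separate step.

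**Other routes and limits.** Section 5.0 lets providers decline Carevix by procedure and gives endometrial biopsy as the example. Section 4.1 makes the provider's willingness to use Carevix an inclusion criterion. Section 11.0 covers patients who consented to Carevix but are then found unsuitable for it. They become ineligible if they do not receive a tenaculum, with an exception for those consented for tenaculum. This implies that some of them can stay in the study as tenaculum subjects.

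**Analysis.** Section 12.0 plans 30 per group and standard tests between groups. It does not mention adjustment or how a tenaculum subject entered the study.

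**The concern.** The control group for the primary pain comparison is not uniquely defined. Under 5.0 and 6.0, a control is someone who comes for a procedure once the control phase has opened. Under 7.0, a control can also be someone who declined Carevix or whose provider did. Under 11.0, a control may be someone judged unsuitable for the device.

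The last two kinds of patient are selected by expectation, anatomy or procedure type, any of which may be related to pain. Carevix subjects, by contrast, are those for whom the device was accepted. Because control places are capped at 30, each such patient also displaces one from the control phase. The control mean would then depend on which section the coordinator follows. If entry route is not recorded at enrolment, the mix may be impossible to reconstruct later.

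**Working it through.** **1. The plan's own figure.** Section 12.0 gives 30 per group, at least 80% power and two-sided 5%, but no difference or SD. The figure can only be inverted:

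- Normal approximation: (1.960 + 0.842) × √(2/30) = 0.723 SD.
- Two-sample t-test: 0.736 SD.

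It can be neither confirmed nor refuted, and the conflict between sections does not depend on it. The counts agree: 25 + 5 + 30 = 60.

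**2. The sections side by side.**

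| Section | Who can be a tenaculum subject | When |
|---|---|---|
| 5.0, 6.0 | Control-arm recruits | After 25 Carevix subjects |
| 7.0, opt-out sentence | Patient or provider opt-outs who agree | Not stated; placed after the exposure-period offer and before the tenaculum-phase sentence |
| 4.1 | Seemingly not provider opt-outs | – |
| 11.0 | Carevix-consented, unsuitable, then tenaculum | Not stated |

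**3. How many opt-outs.** Assumptions, not in the documents: a proportion p of patients offered Carevix opt out, and all of them agree to take part with the tenaculum. While w Carevix subjects accrue, the expected number of opt-outs is k = w × p/(1 − p). Two windows are possible: w = 25 (opt-outs enter throughout the first 25 Carevix subjects) and w = 5 (opt-outs enter only alongside the last five). At p = 30%:

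- w = 25: 25 × 0.3/0.7 = 10.7, which is 36% of 30.
- w = 5: 5 × 0.3/0.7 = 2.1, which is 7% of 30.

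**4. How far the contrast shifts.** Let opt-outs differ from acceptors in mean pain by δ (assumed 0.5 to 1 SD, either direction), and let f = k/30. Control-phase patients are not screened for willingness to use Carevix, so a share p of them would also have opted out.

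- Shift with control-phase controls only: p × δ.
- Shift with opt-outs mixed in: f × δ + (1 − f) × p × δ.
- Difference, which is what the fix removes: f × (1 − p) × δ = (w × p/30) × δ.

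At p = 30% and w = 25, the mixed shift is (0.357 + 0.643 × 0.30) × δ = 0.55δ, the remaining shift is 0.30δ, and the amount removed is 0.25δ.

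| p | w | k of 30 | Shift remaining after fix (SD) | Shift removed (SD) |
|---|---|---|---|---|
| 10% | 25 | 2.8 | 0.05 to 0.10 | 0.042 to 0.083 |
| 10% | 5 | 0.6 | 0.05 to 0.10 | 0.008 to 0.017 |
| 20% | 25 | 6.25 | 0.10 to 0.20 | 0.083 to 0.167 |
| 20% | 5 | 1.25 | 0.10 to 0.20 | 0.017 to 0.033 |
| 30% | 25 | 10.7 | 0.15 to 0.30 | 0.125 to 0.25 |
| 30% | 5 | 2.1 | 0.15 to 0.30 | 0.025 to 0.05 |

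**5. Consequence for the test at p = 30%.** This is the t-test with 30 per group and equal devices, so that the true standardized difference is the shift itself (noncentrality = shift × √15).

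- After the fix: shift 0.15 to 0.30 SD, rejection 9% to 21%.
- Mixed, w = 25: shift 0.275 to 0.55 SD, rejection 18% to 55%.
- Mixed, w = 5: shift 0.175 to 0.35 SD, rejection 10% to 27%.

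**The case against.** **The timing is inferred.** The opt-out sentence in 7.0 carries no date and says that people will be asked, not that they are enrolled. Section 6.0 supplies a window, the last five Carevix subjects, in which an opt-out could join with the tenaculum without breaching the 25-subject rule. This stands as a limit on the claim. A reader might infer that 7.0 expressly enrols controls during the exposure period, but it does not say so. The sequence of sentences points that way, and no passage states the narrower reading. Even on the narrower reading, opt-outs and control-phase patients share one control group.

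**The size rests on assumptions.** This also stands. The documents give no opt-out rate, acceptance rate or pain difference, and at p = 10% or in the five-subject window the avoidable shift is small.

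**Control-phase patients are not a clean baseline.** Correct. A reader might charge the whole opt-out share times δ to the 7.0 route, 0.18 to 0.36 SD at p = 30%. That would treat control-phase patients as if they were all acceptors. They include would-be decliners, so the avoidable part is 0.125 to 0.25 SD.

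**Something may be out of sight.** A figure just before 5.0 is not reproduced in the text available for review. The absence of a rule is therefore claimed for the visible text only.

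**Conclusion.** The point holds as a conflict over who counts as a control. Sections 5.0 and 6.0 set a start rule. Section 7.0, read in sequence, opens a route with no stated delay, cap or separate group. Sections 4.1 and 11.0 pull in different directions on provider opt-outs and on patients unsuitable for the device. Section 12.0 would pool all of them without adjustment.

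The size of any bias cannot be derived from the documents. Under the stated assumptions at p = 30%, the avoidable shift lies between 0.025 SD (five-subject window, δ = 0.5 SD) and 0.25 SD (25-subject window, δ = 1 SD). For scale, 30 per group detects about 0.74 SD with 80% power.

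A reader might go further and conclude that the comparison becomes like-for-like once opt-outs are removed. The documents do not support that: the design is a non-randomized cohort with sequential enrolment, and confounding remains either way. The repair is cheap and is best made before enrolment, because entry route may be hard to recover afterwards.

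**What to change.** 1. Reconcile 4.1, 5.0, 6.0, 7.0 and 11.0 so that patients who enter with the tenaculum through opt-out, or through unsuitability for Carevix, do not count toward the 30 primary controls. State in the same edit whether provider opt-outs meet 4.1 and may be surveyed at all.
2. Record in REDCap, for each tenaculum subject, the entry route (control phase / patient opt-out / provider opt-out / unsuitable for Carevix). Record procedure type for subjects in both groups.
3. In 12.0, base the primary comparison on control-phase tenaculum subjects. Describe the other tenaculum subjects separately and add them in a sensitivity analysis.

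**Cost.** A few sentences, two data fields and one extra analysis. The primary comparison stays at 30 versus 30; any opt-outs surveyed come on top of the 60.

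**Downsides.** Control accrual takes slightly longer, although 15.0 already allows about six months for it. All primary controls come later in calendar time than the first 25 Carevix subjects, so early-period controls are lost from the primary comparison. The fix does not remove the remaining confounding, since control-phase patients are not screened for willingness to use Carevix. The report should say so.
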